8.3 Dose Modification Considerations for Patients Receiving Ipilimumab (Arm 1)

a. Dose and schedule modifications for ipilimumab

There will be no dose reductions for ipilimumab. The dose of ipilimumab will either be given or delayed/discontinued. Patients may develop study drug-related toxicities that may require skipping doses or dose discontinuation. Some of these adverse events may be consistent with potentially drug-related immune-mediated phenomena; termed IRAEs. Details of how to dose study medication in the presence of adverse drug reactions that may or may not be IRAEs are addressed below.

Patients will delay or discontinue treatment with ipilimumab if they experience at least one adverse event, specified below, considered by the investigator to be **definitely, probably, or possibly** related to ipilimumab treatment unless otherwise specified. The following criteria will be used to determine dosing delay, restarting doses, or discontinuing ipilimumab. For an adverse event, review the following criteria in a stepwise manner: First, assess the dose delay criteria and decide whether a scheduled dose should be delayed. Second, determine whether the permanent discontinuation criteria apply to the adverse event in question as well.

NOTE: Due to the possible effect of treatment with ipilimumab on the immunologic response to infectious disease vaccines, patients must not have had any infectious disease vaccination (e.g., standard influenza, H1N1 influenza, pneumococcal, meningococcal, tetanus toxoid) 1 week before or after any dose of ipilimumab.

b. Criteria to delay/skip one dose of ipilimumab

**NOTE: See also: [Section 8.3e](#): Dose Modification and Management for Cardiomyopathy Myocarditis

Delay ipilimumab dosing for any of the following definitely, probably, or possibly treatment related adverse events, unless otherwise specified:

- Grade ≥ 1 diarrhea and/or colitis **regardless of attribution**. Grade ≥ 2 diarrhea and/or colitis, definitely, probably, or possibly related to ipilimumab, requires permanent discontinuation.
- Any other \geq Grade 2 non-skin related adverse event (including IRAEs) except for laboratory abnormalities.

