- Grade ≥ 2 laboratory abnormalities that are secondary to an immune-related adverse event or autoimmune phenomenon (e.g., Grade ≥ 2 TSH associated with a CTCAE v.4 grade 2 thyroid dysfunction induced by ipilimumab, anemia, neutropenia, amylase, lipase, CPK, hyperglycemia, or elevated LFTs) should also lead to an ipilimumab dosing delay/skipping.
- Any other \geq Grade 3 laboratory abnormality.
- Any \geq Grade 3 skin-related adverse event (including IRAEs) **regardless of attribution**.

c. Criteria to resume ipilimumab treatment

**NOTE: See also: [Section 8.3e](#): Dose Modification and Management for Cardiomyopathy Myocarditis

Ipilimumab **may not** be restarted while the patient is being treated with oral or intravenous corticosteroids for the management of immune related adverse events except for patients on stable doses of hormone replacement therapy for adrenal insufficiency such as hydrocortisone. In addition, patients must be off and have no requirement for oral/I.V. corticosteroids for at least 1 week and meet the other criteria for retreatment as outlined below.

Restart ipilimumab dosing if/when the adverse event(s) resolve(s) to \leq Grade 1 severity or returns to baseline within 3 weeks of last dose administration:

- If the adverse event has resolved (to \leq Grade 1 severity or returns to baseline), restart ipilimumab dosing at the next scheduled time point per protocol.
- If the adverse event has not resolved in the protocol-specified dosing window, the next scheduled dose will be omitted.
- Patients with Grade 1 diarrhea and/or colitis who require steroid therapy must have resolution to Grade 0 (or baseline) before resuming dosing with ipilimumab. Patients with Grade \geq 2 related diarrhea and/or colitis must have ipilimumab permanently discontinued.

d. Criteria for permanent discontinuation of ipilimumab for Related Adverse Events

**NOTE: See also: [Section 8.3e](#): Dose Modification and Management for Cardiomyopathy Myocarditis

Ipilimumab administration must be permanently discontinued for any of the following definitely, probably, or possibly treatment related adverse events, unless otherwise specified:

- Any \geq Grade 2 eye pain or reduction of visual acuity that does not respond to topical therapy and does not improve to \leq Grade 1 severity within 2 weeks of starting therapy, OR, requires systemic treatment.

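### Sections 8.3b and 8.3c give opposite instructions when Grade 1 diarrhea or colitis without steroids persists at the next scheduled ipilimumab dose

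*Combined protocol and SAP*

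**What the plan says.** Section 8.3 governs ipilimumab dosing in Arm 1. Doses are not reduced; each is given, delayed or stopped. Section 8.3a asks the site to check the delay criteria first and the permanent-discontinuation criteria second.

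- **Delay (8.3b).** The trigger for this toxicity is "Grade ≥ 1 diarrhea and/or colitis", irrespective of attribution. Other non-skin events start one grade higher: at or above "Grade 2 non-skin related adverse event (including IRAEs) except for laboratory abnormalities". The subsection is headed as criteria to delay or skip one dose.
- **Restart (8.3c).** The general rule begins "Restart ipilimumab dosing if/when the adverse event(s) resolve(s) to" and sets the threshold at Grade 1 or lower, or baseline, within 3 weeks of the last dose. A resolved event is defined by that same threshold, and the instruction is then to "restart ipilimumab dosing at the next scheduled time point per protocol". An event not resolved within the dosing window leads to omission of the next scheduled dose.
- **Restart after steroids (8.3c).** The only restart threshold specific to diarrhea or colitis reads "Patients with Grade 1 diarrhea and/or colitis who require steroid therapy must have resolution to Grade 0 (or baseline") before dosing resumes.
- **Discontinuation (8.3c and 8.3d).** Patients with Grade 2 or higher "related diarrhea and/or colitis must have ipilimumab permanently discontinued".

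**The concern.** For most toxicities a delay rule and a restart rule leave a gap between them, so a patient has to improve before dosing resumes. For diarrhea and colitis the delay trigger is Grade 1 while the general restart threshold still admits Grade 1. A patient whose symptoms have not changed can therefore satisfy both.

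This is the toxicity for which the protocol requires permanent discontinuation at related Grade 2, so how Grade 1 is handled matters for safety. Since there is no reduced dose, the two readings differ by a full 10 mg/kg infusion against none. Two sites could treat the same persistent symptom differently, each with text to support it. The central data review described in Section 18.6, which checks treatment and dose against the protocol, would have no basis for calling either a deviation.

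**Working it through.** The plan states no figure here, so there is nothing numerical to reproduce. The check sets the rules side by side by grade and steroid need.

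**Inputs.** Delay at Grade 1 or higher for diarrhea/colitis (8.3b). Restart at Grade 1 or lower, or baseline, within 3 weeks of the last dose (8.3c, general). Restart at Grade 0 or baseline for Grade 1 patients needing steroids, with at least 1 week off oral or IV steroids (8.3c). Permanent discontinuation for related Grade 2 or higher (8.3c, 8.3d).

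**Step 1: each case on a scheduled dosing day after a delay has begun** (Grade 1 means above baseline)

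| Diarrhea/colitis state | 8.3b delay met? | 8.3c restart met? | Conflict |
|---|---|---|---|
| Grade 0 | No | Yes | No |
| Grade 1, no steroids | Yes | Yes | **Yes** |
| Grade 1, steroids required | Yes | No | No |
| Grade 2 or higher, related | Permanently discontinued | Not applicable | No |
| Unrelated Grade 2 or higher, improved to Grade 1 within the window, no steroids | Yes | Yes | **Yes** |

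**Step 2: comparison with other toxicities.** Other non-skin, non-laboratory events and immune-related laboratory abnormalities delay at Grade 2; skin events and other laboratory abnormalities delay at Grade 3. All have a general restart threshold of Grade 1 or lower, so no grade falls under both rules. Diarrhea/colitis is the only item in the 8.3b list where trigger and restart share a grade.

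**Step 3: search for a tie-breaker.** Section 8.3a orders delay before discontinuation but does not rank delay against restart. Section 8.3d lists reasons for permanent discontinuation. Section 8.3e concerns cardiac events. Section 8.3f lists exceptions that allow resumption, none of them for diarrhea or colitis. The 3-week limit does not settle it, because a persistent Grade 1 event meets the general threshold throughout that window.

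**Step 4: timing.** On the first affected day, 8.3b withholds the dose and 8.3c, which presupposes a delay, points to the next scheduled time point. The two are compatible that day. At the next time point, with Grade 1 still present, 8.3b is triggered again while 8.3c says to dose. That is where they collide.

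**Step 5: reach.** A restart needs an earlier dose. Of the 15 planned infusions (4 induction + 11 maintenance), the conflict can arise at doses 2 to 15, that is 15 − 1 = 14 of them.

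**The case against.** The best defence is that the section is meant to be read in sequence. Section 8.3a puts the delay decision first, 8.3b speaks of skipping one dose, and 8.3c resumes at the next scheduled time point. On that reading 8.3b governs the present dose and 8.3c the following one. This stands for the first affected dosing day. A reader might infer that the two rules contradict each other at the same moment from the outset, or that the Grade 1 safeguard has no effect; the text does not support either, because the sequential reading costs the patient at least the current dose. It does not answer what happens when Grade 1 persists, since 8.3b contains no exemption for a second consecutive occurrence.

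A second defence is that resolving to Grade 1 implies improvement from something worse, so a Grade 1 event that never changed is not resolved. That is arguable, but a persistent Grade 1 event literally meets the threshold, and restricting the Grade 0 requirement to steroid-treated patients implies that the general threshold governs the others. If the defence is accepted, steroid-free Grade 1 is left with no stated restart point except baseline. It also leaves untouched the unrelated higher-grade event that did improve to Grade 1.

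A third is that sites have recourse: 8.3d lets the investigator stop ipilimumab for substantial clinical risk, and Sections 7.0 and 8.8 name a contact for dosing questions. These soften the practical consequence but do not reconcile the rules. Section 8.3 has no general discretion clause of the kind that 8.2b gives for interferon.

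**Conclusion.** The inconsistency is real and narrow. It concerns Grade 1 diarrhea or colitis above baseline, without steroids, still present at the next scheduled dose, including unrelated higher-grade events that have improved only to Grade 1. There the protocol both delays and restarts, and sets no precedence. It can occur at any dose after the first. It should be classed as an internal inconsistency with a patient-safety consequence. No alpha, power or event count changes, and the effect on control-arm exposure cannot be quantified from the documents.

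Two larger readings are tempting and should not be drawn.

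- **Number affected.** A reader might combine the >20% band for diarrhea in the Section 3.2 adverse event list with the 310 ipilimumab patients assumed in Section 11.7b (0.20 × 310 = 62). That band covers any grade at any time, including related Grade 2 or higher, which is discontinued. The 310 is a planning assumption. The share with steroid-free Grade 1 symptoms on consecutive dosing days is not given.
- **Forced removal from treatment.** A reader might infer that omitting dose 4 triggers the 84-day rule in Section 7.4, since Week 10 to Week 25 is 15 × 7 = 105 days. That holds only if an omitted dose counts as a treatment delay, which the protocol does not say.

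**What to change.** Reconcile 8.3b and 8.3c by stating one criterion that ends a delay triggered by Grade 1 diarrhea or colitis not requiring steroids, worded so that the delay trigger and the restart criterion cannot both be met. It should also cover an unrelated higher-grade event that has improved to Grade 1. The clinical threshold is for the sponsor to decide.

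The cost is one sentence in either subsection, with no added visits, tests or procedures. If ipilimumab dosing has already finished, the same sentence can be recorded as a documented interpretation for use in exposure summaries and deviation review.

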- Any \geq Grade 2 diarrhea and/or colitis related to ipilimumab. Any \geq Grade 2 diarrhea/colitis should be considered RELATED unless immune related colitis is definitely ruled out (including by endoscopy and biopsy.)
- Any \geq Grade 2 hypophysitis, pneumonitis, nephritis, and/or sarcoid-like lesions.
- Any new motor or sensory neurologic toxicity \geq Grade 2 regardless of attribution (including Guillain-Barré syndrome and myasthenia gravis).
- Any \geq Grade 3 bronchospasm or other hypersensitivity reaction.
- Any other \geq Grade 3 non-skin adverse event with the exception of events listed under “Exceptions to Permanent Discontinuation”
- AST or ALT $> 5 \times$ ULN.
- Total Bilirubin $> 3 \times$ ULN.
- Any other \geq Grade 4 laboratory abnormalities except for specified exceptions
- Any other \geq Grade 4 adverse event.
- Stevens-Johnson syndrome, toxic epidermal necrolysis, or rash complicated by full thickness dermal ulceration or necrotic, bullous, or hemorrhagic manifestations.
- Any adverse event, laboratory abnormality or intercurrent illness which, in the judgment of the investigator, presents a substantial clinical risk to the patient with continued dosing.
- Patients who require high dose steroids, other immune suppressants or anti-TNF drug therapy for the management of immune related adverse

events as described in the Toxicity Management Guidelines/Algorithms should have ipilimumab permanently discontinued.

e. Dose Modification and Management for Cardiomyopathy Myocarditis

- Drug will be held for Grade 2 cardiac dysfunction pending evaluation
- Drug will be permanently discontinued for Grade 3 or 4 cardiac dysfunction and Grade 2 events that do not recover to baseline or that reoccur
- Treatment with steroids as clinically indicated

Cardiac *	Management/Next Dose for BMS-936558 (Nivolumab) + Ipilimumab Cardiac Toxicities
≤ Grade 1	Hold dose pending evaluation and observation.** Evaluate for signs and symptoms of CHF, ischemia, arrhythmia or myositis. Obtain history EKG, CK (for concomitant myositis), CK-MB. Repeat troponin, CK and EKG 2-3 days. If troponin and labs normalize may resume therapy. If labs worsen or symptoms develop then treat as below. Hold pending evaluation.

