Grade ≥2 with suspected myocarditis	Hold dose.** Admit to hospital. Cardiology consult. Rule out MI and other causes of cardiac disease. Cardiac Monitoring. Cardiac Echo. Consider cardiac MRI and cardiac biopsy. Initiate high dose methylprednisolone. If no improvement within 24 hours, add either infliximab, ATG or tacrolimus. Resume therapy if there is a return to baseline and myocarditis is excluded or considered unlikely.
Grade ≥2 with confirmed myocarditis	Off protocol therapy. Admit to CCU (consider transfer to nearest Cardiac Transplant Unit). Treat as above. Consider high dose methylprednisolone. Add ATG or tacrolimus if no improvement. Off treatment.

*Including CHF, LV systolic dysfunction, Myocarditis, CPK, and troponin
 
**Patients with evidence of myositis without myocarditis may be treated according as "other event"
 
Note: The optimal treatment regimen for immune mediated myocarditis has not been established. Since this toxicity has caused patient deaths, an aggressive approach is recommended.
	

f. Exceptions to permanent discontinuation of ipilimumab

Ipilimumab administration may be resumed in the following cases:

- Potentially reversible inflammation (< Grade 4), attributable to a local anti-tumor reaction and a potential therapeutic response. This includes inflammatory reactions at sites of tumor resections or in draining lymph nodes, or at sites suspicious for, but not diagnostic of metastasis.
- Laboratory abnormalities that are rapidly reversible, not life threatening, do not reflect underlying organ system dysfunction, and are not related to the study treatment, such as transient elevations of uric acid, hypocalcaemia, hypophosphatemia.
- Hospitalization for ≤ Grade 2 adverse events (not including Grade 2 events that require permanent discontinuation) where the primary reason for hospitalization is to expedite the clinical work-up.
- Patients with the following conditions where in the investigator's opinion continuing study drug administration is justified:
 - Ocular toxicity that has responded to topical therapy and has improved to ≤ Grade 1 severity within 2 weeks of starting therapy.
 - Patients without a diagnosis of hypophysitis who have Grade 2 hypothyroidism, Grade 2 low testosterone or Grade 2 adrenal insufficiency where clinical symptoms are controlled with appropriate hormone replacement therapy.

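### Section 8.3e both stops and allows restarting ipilimumab after recovered, related Grade 3–4 cardiac dysfunction when myocarditis was suspected but not confirmed

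*Combined protocol and SAP*

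**What the plan says.** Section 8.3e gives the cardiac rules for ipilimumab twice, as bullets and then as a table.

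- **Bullets.** Grade 2 cardiac dysfunction is held pending evaluation. The next bullet reads "Drug will be permanently discontinued for Grade 3 or 4 cardiac dysfunction and Grade 2 events that do not recover to baseline" and goes on to add Grade 2 events that recur.
- **Table, suspected myocarditis at Grade 2 or higher.** Hold the dose, admit, work up, start high-dose methylprednisolone, and add another immunosuppressant if there is no improvement within 24 hours. The row ends: "Resume therapy if there is a return to baseline and myocarditis is excluded or considered unlikely".
- **Table, confirmed myocarditis at Grade 2 or higher.** Off protocol therapy.
- **Table footnotes.** The cardiac scope is given as "Including CHF, LV systolic dysfunction, Myocarditis, CPK, and troponin". The second footnote begins "Patients with evidence of myositis without myocarditis may be treated according as" and sends such patients to the handling of other events.

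The surrounding text matters too. Section 8.3a limits the delay and discontinuation rules to events definitely, probably or possibly "related to ipilimumab treatment unless otherwise specified", and sets a two-step review: "Second, determine whether the permanent discontinuation criteria apply to the adverse event in question as well". Section 8.3d opens "Ipilimumab administration must be permanently discontinued for any of the following definitely, probably, or possibly treatment related adverse events, unless otherwise specified". Its list includes other Grade 3 or higher non-skin events, and patients who need high-dose steroids, other immune suppressants or anti-TNF drugs for immune-related events. Section 8.3f lists the exceptions to permanent discontinuation; none is cardiac. Sections 8.3b, 8.3c and 8.3d each refer the reader to 8.3e.

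**The concern.** A treating site needs one answer to whether ipilimumab may be given again after a severe cardiac event. Here the bullet and the row give opposite answers for the same patient, and the row's answer is the less cautious. It allows a restart even when myocarditis was only judged unlikely and not ruled out. The table's own note says this toxicity has caused deaths and recommends an aggressive approach.

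Oversight is affected as well. Section 18.6 asks data coordinators to judge whether a patient should be off treatment under the protocol's criteria, and auditors to check compliance with treatment administration. With two opposite criteria, neither can classify such a case.

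**Working it through.** The check is a comparison of text; the plan has no figure to reproduce.

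**Do the bullet and the row cover the same events?** Yes. The bullet concerns cardiac dysfunction. The table's scope footnote names CHF and LV systolic dysfunction. The row's lower limit is Grade 2 and it has no upper limit, so Grades 3 and 4 are inside it.

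**Apply both to each case.**

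| Case (at least possibly related unless stated) | Bullet | Table | Conflict? |
|---|---|---|---|
| Grade 2, recovers, no recurrence, myocarditis unlikely | Restart not barred | Restart | No |
| Grade 3–4, myocarditis suspected then judged unlikely or excluded, recovers | Stop permanently | Restart | **Yes** |
| Grade 3–4, does not recover | Stop permanently | Restart condition not met | No |
| Grade 3–4, myocarditis confirmed | Stop permanently | Off protocol therapy | No |
| Grade 3–4, found unrelated | Outside the attribution limit in 8.3a | Same | No |

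**Does other text decide between them?** No sentence ranks the bullets above the table. Four provisions favour stopping: the bullet itself, the 8.3d rule on related Grade 3 or higher non-skin events, the 8.3d rule on high-dose steroids and other immune suppressants, and the absence of a cardiac exception in 8.3f. The steroid rule bears closely on the row, which orders high-dose methylprednisolone and then permits a restart. It does not settle every case: if myocarditis is excluded, the steroid may not have been for an immune-related event. The 8.3d list also applies unless otherwise specified, and a site could take the more specific 8.3e row as that specification.

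The table heading names nivolumab plus ipilimumab, a combination this trial does not use. That may explain the mismatch, but the table stands as operative text.

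**How many patients?** Section 11.7b assumes 310 patients on ipilimumab, out of 620 eligible in the control arm. The documents give no rate for the affected combination, so these rates are assumptions:

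- 310 × 0.001 = 0.31; 310 × 0.003 = 0.93; 310 × 0.01 = 3.1
- If all 620 chose ipilimumab: 620 × 0.001 = 0.62; 620 × 0.003 = 1.86; 620 × 0.01 = 6.2

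The nearest document figure is in section 3.2c, which lists ipilimumab myocarditis in the column for events under 3%: 310 × 0.03 = 9.3, so fewer than 10. That is not a rate for suspected cases and is shown only for scale.

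**Is anyone still on ipilimumab?** Treatment stops at the end of Year 3 (section 9.2, footnote b). This version is dated November 27, 2023, so anyone who started three years or more earlier, by November 27, 2020, would have finished. Section 11.1 expected accrual to take less than 2.5 years, section 11.5 placed the final RFS analysis in late 2018, and section 18.8 describes enrolment in the past tense with an observed Grade 3–4 irAE rate on ipilimumab. All of this suggests that dosing has ended; no text states it.

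**The case against.** The best reply is that section 8.3, read as a whole, already says stop. The review in 8.3a goes on from delay to discontinuation, 8.3d catches related Grade 3 or higher non-skin events, 8.3f offers no cardiac way out, and the references to 8.3e are worded as additions, not replacements. On that view the row only describes work-up within the limit set by the bullet, and section 8.8 gives a contact for doubtful cases. Much of this stands, and it is why the row is the text to change. It does not remove the conflict, because the row gives an explicit restart instruction with no grade limit.

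A second reply is that the group is close to empty. The row tells sites to rule out infarction and other causes, and an event explained that way is unrelated. The ipilimumab list in section 3.2c does not include CHF or LV systolic dysfunction among possibly related cardiac events. The group is indeed very small. But judging myocarditis unlikely is weaker than excluding it, and a cardiac event that is not myocarditis can still be called possibly related.

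A reader might infer more than the text supports:

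- *That the row permits ipilimumab after confirmed myocarditis.* It does not; the next row takes the patient off treatment.
- *That isolated CPK or troponin rises are part of the conflict, or should be moved to the laboratory rules.* The bullet speaks of cardiac dysfunction and does not say that it covers laboratory findings. The scope footnote keeps these rises in the table, and the second footnote moves out only myositis without myocarditis. In 8.3b, delay starts at Grade 2 for immune-related laboratory abnormalities, with CPK named; "Grade 3 laboratory abnormality" is the threshold only for the others. Moving these rises to 8.3b–d would drop the requirement that myocarditis be excluded or thought unlikely, because 8.3c has no such condition.
- *That patients were re-treated wrongly, or that survival results are affected.* Nothing in the documents shows either.

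**Conclusion.** The conflict is real and confined to one group: Grade 3–4 cardiac dysfunction, at least possibly related to ipilimumab, with suspected but unconfirmed myocarditis and full recovery. The attribution limit comes from 8.3a; the bullet does not repeat it. The row should give way to the bullet, because the rest of section 8.3 agrees with the bullet.

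Severity is minor. On the assumed rates, a handful of patients at most could be affected, and there is no claim about OS or RFS. If ipilimumab dosing has ended, as seems likely, the gain is mainly a consistent protocol. The textual conclusion does not depend on the assumed rates or on the dosing status; its practical importance does.

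**What to change.** In the 8.3e table row for suspected myocarditis at Grade 2 or higher, keep the last sentence, "Resume therapy if there is a return to baseline and myocarditis is excluded or considered unlikely", but limit it to Grade 2 events and make it subject to the steroid rules in 8.3c (at least 1 week off oral or intravenous corticosteroids) and 8.3d. Then add: *Grade 3 or 4 cardiac dysfunction at least possibly related to ipilimumab: permanently discontinue, even if it recovers.*

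Leave the handling of CPK and troponin in the table as it is.

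The cost is the wording of one table row at the next protocol revision, with no new data or analysis. A site notice is needed only if a patient is still receiving ipilimumab.
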